| Primary Objective | To determine the antiproliferative effects of ATB versus placebo as determined by tumor Ki-67. |
| Secondary Objectives | 
 1. Characterize the pharmacokinetics (PK) and pharmacodynamics (PD) properties 2. Determine the biologic correlates of response including NFkB, and RNASeq. |
| Primary Endpoint | Determine the anti-proliferative effects of ATB as determined by tumor Ki-67 in baseline tumor biopsy compared to resected control tumor tissue from untreated patients. |
| Secondary Endpoints | 
 1. PK and PD properties from the saliva samples collected during the period of the study will be calculated. 2. Measure biologic correlates of response including NFkB, and RNASeq from the tumor specimens collected at baseline and on the day of surgery. |
| Study Design | 
This is a window of opportunity study of ATB.
 
The study has been amended from a randomized study of ATB versus placebo to a single arm open label trial of ATB
 |

| | |
|---|--|
| | Upon initiating study treatment, patients will start taking the study drug. The duration of treatment will depend upon scheduling of their surgery—typically from the time surgery is scheduled it will be between seven to 28 days. Four (300 mg) pills will be taken three times per day until the evening prior to surgery. |
| Number of Subjects | Approximately *** subjects will be enrolled to achieve 14 total ATB-treated patients. |
| Estimated Time to Complete Enrollment: | Approximately two years. |

STUDY SCHEMA

STUDY CALENDAR:

| Procedure | Screening ¹ | ATB Administration: (Daily until Day -1 of Surgery) | | End of Treatment | |
|---|--|--|------------------------------------|------------------|-------------------------|
| Study Day/Visit Day | Day – 28 to Enrollment | Day 1 | Prior to Surgery ^{12, 13} | Day of Surgery | Follow Up ¹³ |
| Informed Consent | X | | | | |
| AE Reporting | Recorded from day 1 of the study drug through 30 days after the last dose of study drug (Section 6). | | | | |
| Concomitant Medications ³ | Recorded from signing of the ICF through 30 days after the last dose of study drug. | | | | |
| Physical Exam ² | X | | | X | X |
| Medical History ² | X | | | | |
| Pregnancy Test (Serum or Urine) ^{4, 13} | X | | | | |
| ECOG Performance Status ⁵ | X | | | | |
| Vital Signs per institutional standards | X | | | | |
| Complete metabolic panel ^{6,13} | X | | X | | X |

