| CBC w/ Diff and platelet count ¹³ | X | | X | | |
| PT, INR ¹³ | | | X | | |
| Research saliva samples ⁷ | | See footnote 7 for research saliva sample draw timepoints. | | | |
| Tumor Measurement by Physical Exam | X | | | | |
| Tumor Specimen ⁹ | X | | | X ⁸ | |
| CT ^{9, 8} | X | | X | | |
| MDASI-HN (MD Anderson Symptom Inventory-Head and Neck Survey) ¹³ | | X | X | | |
| ATB administration | | Patient to take as directed from day 1-prior to surgery | | | |
| Patient Diary ¹¹ | | X | X | | |

1. Screening procedures must occur within 28 days prior to registration. ATB administration should start within seven days of registration.
2. Focused physical examination by a study investigator.
3. Capture medications taken from signing of informed consent document until 30 days post last dose of ATB. Medications given during the surgical hospitalization will only be collected if related to Adverse event treatment.
4. For women of childbearing potential.
5. Refer to Appendix 1.
6. Including albumin, total protein, total bilirubin, direct bilirubin, ALT, AST, LDH, alkaline phosphatase, bicarbonate, sodium, potassium, chloride, creatinine, , calcium, BUN, and glucose.
7. A total of at least two patient samples (saliva) per day will be collected (predose, before lunch, or before dinner dose 1, dose 2, dose 3 of study drug). Saliva samples will be collected in a 5-ml bio vial, time documented by the patient, then frozen and stored by the patient until collection (see Section 3.1 for more details).
8. Fresh frozen tumor specimen will be collected, see section 5.6 for processing.
9. CT at baseline may be performed within six weeks prior to study registration. CT at day -1 of surgery can have a window of - 3 days. If baseline tumor is not measurable by baseline imaging (eg due to dental artifact) then follow-up imaging is NOT required
10. Patient will complete study diary with all relevant information and will submit the diary to study coordinator on the day of surgery.
11. The date for follow-up assessment is at the discretion of the surgeon and will correspond with the first post-operative outpatient assessment.
12. The indicated assessment for this timepoint will be collected only once with a window of two days: Day -3 to Day 0 of surgery.

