3 STUDY DESIGN

3.1 General Description

A window of opportunity (WOO) Clinical Trial permits examination of drug effects on cancer patients during the “window” between diagnosis of their cancer and their definitive cancer surgery. Similar to the phase 0 study design, the WOO trial design permits examination of the biologic effects of a drug. This is a single arm, open-label window of opportunity study of ATB.

Upon initiating study treatment, patients will start taking study drug. The duration of treatment will depend upon scheduling of their surgery—typically, from the time surgery is scheduled, it will be between seven to 28 days. Four (300 mg) pills will be taken three times per day until the evening prior to surgery. A pill diary will be completed by the patient.

While taking study medication, patients will be required to provide saliva samples. Patients will be given specimen tubes and will store collected samples in the freezer. Saliva sample tubes will be prelabeled to reflect the time of collection (Dose 1- morning, Dose 2-midday and Dose 3- evening). The patients’ diaries will contain checkbox reminders for daily saliva collection. Approximate 1 ml of saliva will be collected. Participants will store collected saliva in storage container provided by the study coordinator in their home freezer.

At the end of the course of therapy, patients will be asked to return the storage specimens to the study coordinator. Patients will be given a Styrofoam transportation container with freeze packs for this purpose. All the specimens will be collected on the day of their surgery.

Saliva samples (1 ml) will be collected at the following timepoints: day 1: then to the evening of the day prior to surgery: A total of at least two patient samples (saliva) will be collected daily corresponding to agent dose timepoints (Dose 1- morning, Dose 2-midday or Dose 3- evening). Saliva samples will be collected in a 5-ml bio vial, time documented by patient, and then frozen and stored by the patient until collection. Patients will be given supplies for saliva collection, storage, and for transportation at the end of the collection period. Compliance of $\geq 90\%$ saliva sample collection is deemed acceptable. Sample storage will be in an airtight container at 0 to - 20° C until batch shipment to [name] laboratory at the University of Houston. The blood, saliva, and tumor tissue specimen should be shipped in dry ice to the following location:

[name]

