4.5 Eligibility Criteria

Study staff must adhere to MCWCC CTO SOPs regarding eligibility review/confirmation.

No waivers of protocol eligibility will be granted. When clinical factors relating to an eligibility item are unclear or questionable, the study PI ([name], [contact]) can only provide guidance or clarification on eligibility.

Inclusion Criteria

Each subject must meet all the following inclusion criteria to be enrolled in the study:

1. Voluntary written consent must be given before performance of any study-related procedure not part of standard medical care, with the understanding that consent may be withdrawn by the subject at any time without prejudice to future medical care.
2. In the event that the diagnosis of SCC is made by an outside pathologist, hence not verified, the patient can start study agent administration but histological confirmation of squamous cell cancer (SCC) of the oral cavity (or histologic variants of SCC) by an MCW pathologist must happen within seven days of registration in order to continue protocol therapy*.
3. Clinical stage I-IVA (as defined by the AJCC, 8th Edition) and amenable to surgical resection.
4. New diagnosis of oral SCC, new second primary, or recurrent oral SCC following a minimum remission of six months following previous definite surgery.
5. History and physical examination by an otolaryngologist and medical oncologist within 28 calendar days of study registration.
6. Zubrod/ECOG Performance status ≤ 2 .
7. Age ≥ 18 years.
8. CBC/differential obtained within 28 calendar days prior to registration, with adequate bone marrow function defined as follows:
 - Absolute neutrophil count (ANC) $\geq 1,500$ cells/mm³;
 - Platelets $\geq 100,000$ cells/mm³;
 - Hemoglobin ≥ 8.0 g/dl (Note: The use of transfusion or other intervention to achieve Hgb ≥ 8.0 g/dl is acceptable).
9. Adequate renal and hepatic function within 28 calendar days prior to registration, defined as follows:
 - Serum creatinine < 1.5 mg/dl or creatinine clearance (CCr) ≥ 50 ml/min within 14 calendar days prior to registration, determined by 24-hour collection or estimated by Cockcroft-Gault formula:
 - $CCr \text{ male} = [(140 - \text{age}) \times (\text{wt in kg})]$
 - $[(\text{Serum Cr mg/dl}) \times (72)]$
 - $CCr \text{ female} = 0.85 \times (CrCl \text{ male})$

CRC Initials: _____

Date: _____

Investigator/Enrolling Physician Initials: _____

Date: _____

10. Total bilirubin < 2 x the institutional ULN;

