11. AST or ALT ≤ 3 x the institutional ULN;
12. Calcium, glucose, potassium, and sodium within 28 calendar days prior to registration, with the following required parameters:
- - Calcium: > 7 mg/dl or < 12.5 mg/dl;
 - Glucose: > 40 mg/dl or < 250 mg/dl;
 - Potassium: > 3 mmol/L or < 6 mmol/L;
 - Sodium: > 130 mmol/L or < 155 mmol/L.
13. Female subjects must meet one of the following:
- Postmenopausal for at least one year before enrollment,
OR
 - Surgically sterile (i.e., undergone a hysterectomy or bilateral oophorectomy), OR
 - If subject is of childbearing potential (defined as not satisfying either of the above two criteria), agrees to practice two acceptable methods of contraception (combination methods require use of two of the following: diaphragm with spermicide, cervical cap with spermicide, contraceptive sponge, male or female condom, hormonal contraceptive) from the time of signing of the informed consent form through 21 days after the last dose of study agent, OR
 - Agrees to practice true abstinence when this is in line with the preferred and usual lifestyle of the subject. (Periodic abstinence [e.g., calendar, ovulation, symptothermal, postovulation methods] and withdrawal are not acceptable contraception methods.)
14. Male subjects, even if surgically sterilized (i.e., status postvasectomy), must agree to one of the following:
- Practice effective barrier contraception during the entire study period and through 60 calendar days after the last dose of study agent,
OR
 - Agree to practice true abstinence when this is in line with the preferred and usual lifestyle of the subject. (Periodic abstinence [e.g., calendar, ovulation, symptothermal, postovulation methods] and withdrawal are not acceptable methods of contraception.)
15. Enrollment on an interventional postoperative study is allowed if study agents do not overlap.
16. Gastric tube drug administration is permissible.

* Note: patients whose confirmatory biopsy fails to demonstrate invasive carcinoma will be excluded from continued participation in the study and considered a screen failure.

CRC Initials: _____

Date: _____

Investigator/Enrolling Physician Initials: _____

Date: _____

Exclusion Criteria

Patients meeting any of the following exclusion criteria are not to be enrolled in the study:

1. Pregnant or lactating women are ineligible due to unforeseeable risks to embryo or fetus.
2. Concurrent use of any medicinal botanical, natural, or other herbal compounds.

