5.7 Dose Modifications

As indicated in the study calendar, a complete metabolic panel (including LFTs) will be performed midway during the course of ATB. Adverse events will be graded according to CTCAE v.5.

| Adverse Event (CTCAE, v. 5) | Action |
|---|---|
| Non-hematological, grade 1 or 2 | Continue ATB therapy at full dose prescribed. Apply maximum supportive care recommendations. If persistent duration of grade 2 adverse event is affecting quality of life, a one-time decrease of 25%. |
| Non-hematological, grade 3 or 4 | Apply maximum supportive care recommendations. Hold ATB therapy until recovery to grade ≤ 1 (up to 14 days). If concomitant elevation of AST/ALT 3 times the upper limit of normal and bilirubin elevation two times the upper limit of normal (Hy's Law criteria) the patient must be removed from study treatment, ATB must be permanently discontinued. If recurrence of adverse event after drug hold and/or interruptions is observed and maximum supportive care measures applied, a dose reduction by 25% is recommended. |
| Non-hematological, grade 3 or 4 and adverse events NOT resolved to grade ≤ 2 within a maximum of 14 calendar days from last planned administration | Dose reductions by 25% will be considered after maximum supportive care recommendations are introduced. |

| Dose Level | Dose |
|------------|-------------|
| -1 | 900 mg TID |
| 0 | 1200 mg TID |

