8.5 Stopping Rule

A temporary suspension of the study will be mandated if any serious toxicity (grade ≥ 3) that occurs during or within 30 days of drug administration and that is definitely, probably, or possibly related to the study drug. Resumption of the study will be permissible following DSMC review and approval.

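### The mandatory Hy's Law stop in section 5.7 is written only in the grade 3-4 cell, so a grade 2 case could literally fall under the instruction to continue dosing (minor; cheap safety fix)

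*Combined protocol and SAP*

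**What the plan says.** The table in section 5.7 is entered by CTCAE v5 grade. For non-hematological events of grade 1 or 2 the action is "Continue ATB therapy at full dose prescribed", with supportive care and a single 25% reduction if a persistent grade 2 event affects quality of life. The row mentions neither liver tests nor the row below it.

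For grade 3 or 4, the cell tells staff to hold ATB until recovery. The same cell then carries the liver rule, which starts "If concomitant elevation of AST/ALT 3 times the upper limit of normal and bilirubin elevation two times the upper limit of normal (Hy's Law criteria" and requires removal from study treatment and permanent discontinuation. The rule appears nowhere else in the protocol.

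Four other places bear on it:

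- Section 4.5, criteria 10 and 11, sets the entry limits: "Total bilirubin < 2 x the institutional ULN" and "AST or ALT ≤ 3 x the institutional ULN".
- Section 8.5 opens "A temporary suspension of the study will be mandated if any serious toxicity (grade ≥ 3", so the study-level suspension also begins at grade 3.
- The Study Calendar schedules the metabolic panel at screening, prior to surgery and at follow-up. Footnote 12 says the pre-surgery assessment "will be collected only once with a window of two days: Day -3 to Day 0 of surgery".
- Section 4.6 lists unacceptable adverse events as a reason to end treatment. It also has the investigator withdraw a subject whose best interests are no longer served by continuing.

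**The concern.** The rule is triggered by two multiples of ULN, but it sits in a cell that is reached by grade. These are different scales. If the trigger can be met below grade 3, a coordinator who grades both tests as 2 and reads across the grade 1-2 row finds an instruction to continue and no pointer to the stop. This is the protocol's only compulsory liver stop for an individual patient. What is at stake is continued dosing of a patient whom the protocol itself says must stop. The primary endpoint, the power and the analysis are not affected.

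**Working it through.** **1. Does a gap exist?** Let A and B be the multiples of ULN at which CTCAE v5 grade 3 starts for AST/ALT and bilirubin. Neither is printed in the documents, so both are assumptions. The trigger is AST/ALT at 3 times and bilirubin at 2 times ULN (section 5.7). A patient can meet it with both tests below grade 3 only if A > 3 and B > 2.

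| Assumed A | Assumed B | Result |
|---|---|---|
| 3 | 2, 2.5 or 3 | no gap |
| 4 or 5 | 2 | no gap |
| 4 | 2.5 | gap: AST/ALT 3 to 4, bilirubin 2 to 2.5 times ULN |
| 5 | 3 | gap: AST/ALT 3 to 5, bilirubin 2 to 3 times ULN |

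The entry limits give indirect support for cut-offs no lower than the trigger. If grade 3 began below 3 times or 2 times ULN, an eligible patient could start treatment already in the hold row. This does not exclude cut-offs exactly at those limits. The match between entry limits and trigger is also loose, because criterion 11 says AST or ALT and so, read strictly, constrains only one enzyme.

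**2. Would another rule catch the patient?**

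| Provision | Applies to a grade 2 trigger case? |
|---|---|
| 5.7, grade 1-2 row | Yes, and says continue |
| 5.7, grade 3-4 cell | Not by grade |
| 8.5 suspension | No, starts at grade 3 |
| 6.1.2 and Table 4 | Only if judged medically important, and then only reporting |
| 4.6 | Yes, through the investigator's judgment; no liver values named |

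**3. Extra exposure.** The calendar row is "Complete metabolic panel ^{6,13} | X | | X | | X", so the pre-surgery panel is the only scheduled one on treatment. Dosing is described as "Four (300 mg) pills will be taken three times per day until the evening prior to surgery", at 4 × 300 = 1,200 mg per dose. Suppose the panel falls on Day -d and the result is known before that day's first dose. The doses remaining are then 3 × d:

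- Day 0: 0 doses.
- Day -1: 3 doses (3,600 mg).
- Day -2: 6 doses (7,200 mg).
- Day -3: 9 doses (10,800 mg).

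Nine doses are 9/84 = 11% of a 28-day course. They are 9/21 = 43% of a 7-day course, but that figure pairs the earliest panel day with the shortest course. Section 5.7 also speaks of a panel midway through treatment, which the calendar does not schedule. If one were done halfway through a 28-day course, 14 × 3 = 42 doses would remain.

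**4. Frequency.** No rate for the gap itself can be derived from the documents. A crude ceiling for something much broader comes from section 1.4, which reports no liver side effects in 300 participants. The one-sided 95% upper bound is 1 - 0.05^(1/300) = 0.0099 per patient for any liver side effect. For 14 patients, 1 - (1 - 0.0099)^14 = 0.13. At assumed rates of 0.1% and 0.01% the same formula gives 1.4% and 0.14%. Trigger cases below grade 3 would be a subset of these.

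**The case against.** The strongest reply is that the intent is clear. The rule says must, gives its own thresholds and names Hy's Law, and a specific mandatory rule normally overrides a general instruction to continue. That stands as a reading of intent. A reader might infer that the plan means to keep dosing Hy's Law patients, and the documents do not support that. What remains is that a compulsory stop depends on the reader making this inference.

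Second, the existence of the gap rests on cut-offs that the documents do not contain. This is correct and is why the point is conditional. The change does no harm if there proves to be no gap.

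Third, section 6.2.1 asks that findings with a common underlying pathology be recorded, when possible, as one event, and a combined liver event might be graded higher than 2. It might, but the section does not say how such an event would be graded, so the conflict remains.

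Fourth, the investigator's duty under section 4.6 would probably lead to withdrawal. That is likely, but it turns an automatic stop into a matter of judgment.

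Fifth, a reader might infer that a patient with rising tests passes through the gap first. That does not follow. The trigger needs both values, and AST/ALT may reach grade 3 before bilirubin reaches 2 times ULN. Such a patient is already in the right row.

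Finally, the 13% should not be read as the chance of a gap case. It is an upper bound for any liver side effect, taken from a six-month study at 4,800 mg/d whose toxicity was described only qualitatively. This trial gives 3,600 mg/d for at most 28 days and excludes severe active liver disease. Section 7.2 also shows that patients were treated before this amendment, so a wording change now would protect fewer than 14.

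**Conclusion.** The point holds as a minor placement defect. The text alone establishes that the only compulsory liver stop sits in the grade 3-4 cell and that the grade 1-2 row says continue without exception. The consequence is conditional: a grade 2 patient who meets the trigger is literally continued only if grade 3 starts above 3 times ULN for AST/ALT and above 2 times ULN for bilirubin. In that case section 8.5 does not help and only judgment under section 4.6 does. The expected frequency is very low, though not purely hypothetical, since section 1.4 mentions a few patients with jaundice in the 24,275-patient study. On the calendar as written, 0 to 9 doses are at issue per affected patient. This is a cheap improvement in patient safety. It has no bearing on the primary endpoint or the sample size.

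**What to change.** Take the Hy's Law sentence out of the grade 3-4 cell. Give it its own row, or a statement above the table, triggered by AST/ALT at 3 times ULN with bilirubin at 2 times ULN at any CTCAE grade, and say that it overrides the grade-based rows. This is one wording change at the next amendment, with no added tests, visits or patients. The possible downside is a rare extra discontinuation.

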5 TREATMENT PLAN

5.1 ATB Administration

ATB will be administered on an outpatient basis. ATB will be administered at a dose of 1,200 mg three times per day (roughly spaced every eight hours) as has been studied for ATB in

human oral leukoplakia trials and in esophageal cancer prevention trials. ATB may be taken with or without food.

| Regimen Description | | | | | | |
|---|-------------|----------------------------|--------------------------------|-------|----------|------------------------|
| ARMS | Study agent | Premedication; precautions | Dose | Route | Schedule | Duration |
| ARM 1 | ATB | None | 1,200 mg, Three times a day | Oral | Daily | 7-28 days ^a |
| a. Total duration depends upon scheduling of surgery. ATB administration must not exceed 28 days. | | | | | | |

- Patient must submit completed study diary to the study coordinator.

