7.3 Missing Data

Data from patients who withdraw from the study, including AEs and any follow-up, will be included in the analyses of primary and secondary outcomes. Patients who are not able to complete at least 50% of planned therapy will be replaced.

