7.4 Data Quality, Analysis Plan

[name] will perform drug quality assurance review with the goal of evaluating protocol compliance. Participants whose compliance with the study drug is $\geq 75\%$ of the prescribed dose will be deemed within an acceptable variation for inclusion of the study analysis.

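### The two grade 3–4 rows in section 5.7 use different recovery grades and an ambiguous 14-day clock, and give no general stop for a patient who does not recover

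*Combined protocol and SAP*

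**What the plan says.** The adverse-event table in section 5.7 has three rows, all for non-hematological events.

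- **First row, grade 1 or 2.** Full dose continues. A single 25% decrease is allowed when a lasting grade 2 event affects quality of life.
- **Second row, grade 3 or 4.** The instruction is "Hold ATB therapy until recovery to grade ≤ 1 (up to 14 days". A 25% reduction is recommended if the event comes back after a hold. If the combined AST/ALT and bilirubin (Hy's Law) criteria are met, "the patient must be removed from study treatment, ATB must be permanently discontinued".
- **Third row, grade 3 or 4 without recovery.** It applies to "adverse events NOT resolved to grade ≤ 2 within a maximum of 14 calendar days from last planned administration". Its action is "Dose reductions by 25% will be considered after maximum supportive care recommendations are introduced".

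The dose-level table gives 1,200 mg three times daily and one lower level, 900 mg three times daily.

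Other sections bear on this:

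- Section 5.1 sets a course of 7 to 28 days depending on the surgery date: "ATB administration must not exceed 28 days". Section 3.1 has dosing run to the evening before surgery.
- Section 4.6 lets treatment end for an unacceptable adverse event or on the investigator's judgment. It also says that treated subjects later withdrawn or discontinued from the study are not replaced.
- Section 7.3 says "Patients who are not able to complete at least 50% of planned therapy will be replaced".
- Section 7.4 accepts patients who took at least 75% "of the prescribed dose will be deemed within an acceptable variation for inclusion of the study analysis".
- Section 8.5 suspends the whole study for serious toxicity, marked as grade 3 or higher, that is at least possibly related to ATB. The suspension lasts until the DSMC approves resumption.

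**The concern.** The second and third rows appear to describe the same patient at successive moments: first the hold, then the hold that did not work. Read in that order, the rules loosen as the outcome gets worse. A patient who recovers to grade 1 may restart. A patient still at grade 3 or 4 after 14 days has failed that condition, yet the only instruction left concerns a lower dose. The recovery grade also shifts from 1 to 2 between the rows, so a patient at grade 2 belongs to neither.

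At stake is patient safety in the days before a cancer operation, and consistent handling across patients. Two investigators could follow section 5.7 in good faith and do opposite things.

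**Working it through.** This is a check of rule logic, with some arithmetic on how far it can reach.

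**Step 1. The plan's dose figure.** 1,200 mg × (1 − 0.25) = 900 mg, or three 300 mg tablets. This matches level −1. The daily dose falls from 3 × 1,200 = 3,600 mg to 3 × 900 = 2,700 mg.

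**Step 2. Each grade at day 14 of a hold**, taking the third row's clock to start at the last dose before the hold (reading A):

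| Grade at day 14 | Second-row recovery (≤1) met? | Third row (not ≤2) applies? | Instruction |
|---|---|---|---|
| 0 or 1 | yes | no | hold ends |
| 2 | no | no | none |
| 3 or 4 | no | yes | 25% reduction considered |

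The first row does not clearly fill the grade 2 gap. It does not mention events that began at grade 3 or 4, and using it would undo the second row's requirement of grade 1 or lower.

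**Step 3. The other clock.** If the third row's 14 days run from the final scheduled dose before surgery (reading B), no doses remain to be reduced and the row has no effect. The second row then stands alone, and it does not say what follows a 14-day hold that ends without recovery.

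**Step 4. Which courses are exposed under reading A.** Let L be the planned course in days (7 to 28) and d the last full-dose day before the hold. Assume 14 full days off drug and an unchanged surgery date.

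- Reduced-dose days left = L − d − 14, which must be at least 1.
- With d ≥ 1 this needs L ≥ 16, so 13 of the 22 whole-day lengths from 7 to 28.
- For L = 28, d can be 1 to 13. The days left run from 28 − 1 − 14 = 13 down to 28 − 13 − 14 = 1.

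**Step 5. How much of the plan such a patient receives, for L = 28.** Dose fraction = [d + 0.75 × (L − d − 14)] / L.

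- d = 1: (1 + 9.75)/28 = 38.4%.
- d = 13: (13 + 0.75)/28 = 49.1%.
- With restart on the 14th day (13 days off) and d = 14: (14 + 0.75)/28 = 52.7%.
- Counted in treatment days with 14 off: 14/28 = 50% exactly.

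**Step 6. Whether another section supplies the missing rule.** Section 4.6 names unacceptable events and judgment, with no grade or time limit. Section 8.5 acts on the study and sets no grade at which a patient may restart. The only mandatory permanent stop in section 5.7 is the liver criterion.

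**The case against.** The strongest reply is that the contradiction depends on one reading of the clock. Taken literally, the last planned administration is the final scheduled dose, and then the third row permits nothing. This stands, and the conclusion has to be conditional on it. But a row with no effect is also a reason to rewrite it.

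Second, the third row only has a reduction considered. It neither orders dosing nor lifts the hold, and it may simply name the dose to use if treatment resumes. That is fair. A reader might infer that the plan directs re-dosing during an unresolved grade 3–4 event; it does not.

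Third, section 8.5 may do more than it first appears to. If its parenthesis defines serious as grade 3 or higher, every related event reaching the third row has already suspended the study. Unrelated events would then be the main group left, and for them the safety case for stopping ATB is weakest. The text supports either reading, and the fix should allow for this.

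Fourth, reported toxicity is low. Section 1.4 describes no observed toxicity in the six-month study with 300 participants randomized to ATB at 4,800 mg per day, and section 5.8 says few side effects are known. This stands: the problem should be rare.

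**Conclusion.** Section 5.7 should be corrected, but the defect is one of wording with limited reach. The two grade 3–4 rows use different recovery grades, the third row's clock is unclear, and no row says when a patient who does not recover must stop, apart from the liver criterion. On reading A, a patient who failed the restart condition could be considered for 900 mg three times daily before surgery, and grade 2 at day 14 has no instruction. This can arise only in courses of 16 to 28 days, with at most 13 reduced-dose days, assuming 14 full days off and a fixed surgery date. On reading B the row does nothing.

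Three stronger inferences are not supported.

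- **That such a patient always ends below half of the planned course.** Step 5 gives 52.7% if dosing restarts on the 14th day, and exactly 50% if days are counted. The plan does not say whether section 7.3 counts doses or days, or whether the prescribed dose in section 7.4 includes a prescribed hold.
- **That the patient would simply be replaced.** Sections 4.6 and 7.3 point in different directions.
- **A probability that someone in the trial is affected.** The documents give no rate for grade 3–4 events lasting 14 days. The summary says only that "subjects will be enrolled to achieve 14 total ATB-treated patients", and section 7.2 indicates that some patients were treated before the amendment, so fewer than 14 may still be enrolled under the changed text.

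**What to change.** Reword the two grade 3–4 rows of section 5.7 so that together they say:

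1. Grade 1 or lower is the only restart threshold. ATB may restart, at full dose or at 900 mg three times daily, only once it is reached.
2. The 14 days run from the last dose taken before the hold.
3. If grade 1 or lower is not reached by then, ATB is permanently discontinued. This settles grade 2 at day 14 as well. The stop may be limited to events at least possibly related to ATB, so that a tumor symptom unlikely to resolve before surgery does not force it. The restart threshold would still apply to all events.

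The existing Hy's Law stop stays as it is.

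The cost is an edit to two table rows, with no change to sample size, visits or endpoints. The downside is a rare extra discontinuation. Whether that patient would be replaced is unclear while sections 4.6 and 7.3 disagree, so one sentence reconciling them could go into the same amendment.
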